12.3 PROCEDURES FOR REPORTING ADVERSE EVENTS

Subjects will be instructed to inform clinic personnel of AE that may arise during the course of the study. Treatment of any AE will be administered under the direction of a physician at Tamshui Mackay Memorial Hospital.

All symptoms will be recorded by clinical staff and will be reviewed by the Principal Investigator/Sub-Investigator prior to any subsequent dosing.

When appropriate, medical tests and examinations will be performed to document resolution of the event(s).

All SAE, whether or not the event is deemed drug-related, will be reported to the Sponsor by telephone within twenty-four hours of PPC's being aware of SAE, followed by a written report within seven days. PPC will be responsible for notifying the IRB and regulatory agencies, if applicable.

The following Sponsor personnel are to be contacted at the occurrence of a SAE:

General Manager, [REDACTED] / Intech Biopharm Ltd.
[name]
ROC
[contact]
[contact]

12.4 PREGNANCY REPORTING

If the female subject or the partner of a male subject becomes pregnant while receiving the investigational drugs or within 30 days after the completion of the last dose of study drug, a pregnancy report form should be completed and expeditiously submitted to the sponsor to facilitate the outcome follow-up. Information on the status of the mother and child will be forwarded to the sponsor. Generally, follow-up will be no longer than 6 to 8 weeks following the estimated delivery date. Any premature termination of the pregnancy will be reported.

While pregnancy itself is not considered to be an AE or SAE, any pregnancy complication or elective termination of a pregnancy for medical reasons will be recorded as an AE or SAE and will be followed as described in Section 12.

An abortion, whether accidental, therapeutic, or spontaneous, should be always reported as an SAE. Similarly, any congenital anomaly/birth defect in a child born to a patient exposed to the study drug should be recorded and reported as an SAE.

13. BIOANALYTICAL ANALYSIS

Bioanalytical procedures will be performed according to PPC SOP.

13.1 ANALYTICAL PROCEDURES

Data management, quality review and reporting of study data pertaining to laboratory analysis of study data will be the responsibility of PPC.

13.1.1 SAMPLES TO BE ASSAYED

In general, single batch of each sample will be all analyzed for drug concentration. Samples from subjects being analyzed will be defined prior to sample analysis

13.1.2 ANALYTE(S) IN BIOLOGICAL MATRIX

Plasma samples will be assayed and reported at the actual sampling time points (or scheduled sampling time points) for albuterol using a validated analytical method according to the principles of FDA GLP Title 21 Part 58.

14. PHARMACOKINETIC AND STATISTICAL ANALYSIS

14.1 PHARMACOKINETIC ANALYSIS DATA SET

The data from the following subjects will be included in the final PK and statistical analysis:

1. Subjects who complete all study periods without major/suspect protocol deviation.
2. Subjects who have missed samples that have been determined prior to the start of bioanalytical analysis as not significantly impacting the overall outcome of the study.

Data from subjects who are dismissed or withdraw due to AE will not be included in the final PK and statistical analysis. The data for these subjects will be presented separately.

Any decision to exclude data from the final data set will be provided with a detailed explanation and will be properly recorded and dated.

The final data set will be defined prior to sample analysis.

14.2 ANALYSIS OF DATA

PK and statistical analysis will be performed on all data from all subjects in the final data set.

14.2.1 PHARMACOKINETIC ANALYSIS

The following PK parameters shall be estimated (where possible and appropriate) included in the PK and statistical analyses for the subjects in the final data set:

C_{max} :	The maximal observed plasma concentration.
T_{max} :	Time when the maximal plasma concentration is observed.
AUC_{0-t} :	Area under the concentration-time curve from time zero until the last measurable concentration or last sampling time t , whichever occurs first. AUC_{0-t} is estimated using the trapezoidal method.
$AUC_{0-\infty}$:	Area under the concentration-time curve from time zero to infinity, calculated as $AUC_{0-t} + C_{last}/\lambda$, where C_{last} is the last measurable concentration.
$k_{el}(\lambda)$:	Terminal elimination rate constant, estimated by linear regression analysis of the terminal portion of the ln-concentration vs. time plot.
$T_{1/2}$:	Terminal elimination half-life, estimated as $\ln(2)/\lambda$.
MRT:	Mean residence time

If a subject's pre-dose concentration is less than or equal to 5% of the C_{max} value for that subject in the given period, then the subject's data without any adjustments can be included in all PK measurements and calculations. If the pre-dose value is greater than 5% of the C_{max} , data from that subject will be dropped from the PK and statistical analysis. Data for subjects dropped due to higher than 5% of C_{max} pre-dose concentrations will be included in a separate appendix in the final study report.

During PK and statistical analyses, drug concentrations below the lower limit of quantitation (BLQ) of an assay will be considered as zero except when they occur between two non-BLQ concentrations.

Missed samples and non-reportable concentrations (e.g. quantity not sufficient) from the analytical laboratory will be treated in the PK analysis as if they had not been scheduled for collection.

The k_{el} , $T_{1/2}$, and $AUC_{0-\infty}$ parameters will not be estimated for plasma concentration-time profiles where the terminal linear phase is not clearly defined.

For subjects with missing or non-reportable concentrations for three or more of the last samples, only the AUC_{0-t} , C_{max} and T_{max} will be presented and included in the statistical analysis (if applicable).

14.2.2 STATISTICAL ANALYSIS

PK and statistical analyses will be performed using SAS® Version 9.2 or higher by PPC.

Descriptive statistics of all PK parameters (min, max, median, mean, SD and CV) will be provided for the test and reference products.

ANOVA including sequence, subjects nested within sequence, period and treatment will be performed on the log-transformed data for AUC_{0-t} , $AUC_{0-\infty}$ and C_{max} and on the raw data for T_{max} , k_{el} and $T_{1/2}$. T_{max} will be analyzed using an additional non-parametric test (Wilcoxon test).

For albuterol, the 90% CI of the Test/Reference ratios of geometric means for AUC_{0-t} , $AUC_{0-\infty}$ and C_{max} will be calculated based on the LSMEANS and ESTIMATE of the ANOVA.

Additional statistical and alternate tests will be performed if necessary.

14.2.3 MISSING DATA

During PK and statistical analyses, treatment of missing data will follow PPC's SOP.

14.3 BIOEQUIVALENCE CRITERIA

Bioequivalence will be demonstrated under fasting conditions if the 90% CI for the Test/Reference ratios of geometric means for AUC_{0-t} , $AUC_{0-\infty}$ and C_{max} are completely contained within the FDA defined acceptance range of 80.00%-125.00%.

15. ETHICAL CONSIDERATIONS

15.1 BASIC PRINCIPLES

This research will be carried out in accordance with GCP as set out by the ICH, the basic principles defined in the U.S. Code of Federal Regulations (21 CFR Part 320), Guideline for GCP and the principles enunciated in the most recent version of the World Medical Association Declaration of Helsinki.

15.2 INSTITUTIONAL REVIEW BOARD

This Protocol and the ICF will be reviewed and approved by the IRB prior to the initiation of the study. The board is constituted and operates in accordance with ICH Harmonized Tripartite Guideline (GCP Consolidated Guideline).

15.3 INFORMED CONSENT FORM

The ICF will be approved by the IRB and a copy will be included in the final report. The ICF will be signed by each subject prior to the study procedure. Each subject will be provided with verbal and written information, in non-technical terms, which will describe the nature and duration of the study. Prior to signing the ICF, subjects will be allowed adequate time to consider the potential benefits and risks associated with their participation in the study. Signed and dated ICFs will be retained with the study records. Subjects/Volunteers will be provided a copy of their signed and dated ICF.

15.4 REVISIONS AND/OR AMENDMENTS TO THE PROTOCOL

Revisions and/or amendments to the protocol must be documented and approved by the Principal Investigator and Sponsor. If the revision/amendment will affect subject safety and/or study design, then the amendment will be re-submitted to the IRB for approval. Administrative changes (i.e., change of analytical facility, typographical errors, discrepancies, clarifications) will also be submitted to the IRB. A copy of the IRB's approval documents will be included in the final report.

For revisions or amendments to the protocol that substantially alter the study design after initiation of the study, the Principal Investigator and Sponsor will decide whether a revised ICF will be needed for continued participation.

It is the Sponsor's responsibility to submit, or to assign responsibility to submit, all revisions and amendments to the appropriate regulatory authorities when necessary.

If an amended or revised version of the ICF is introduced during the study, each subject's further consent should be obtained.

15.5 INVESTIGATOR RESPONSIBILITIES

The Principal Investigator is responsible for ensuring that the clinical study is performed in accordance with the protocol, the current revision of the Declaration of Helsinki, ICH GCP guidelines and applicable regulatory requirements.

15.6 STUDY COMPLETION/TERMINATION

PPC and/or the Sponsor reserve the right to terminate the study at any time, and for any reason.

15.7 SPONSOR VISITS

The Sponsor is encouraged to visit PPC and clinical facility, if desired, and at their convenience. The Principal Investigator and staff will provide, if requested, all source documents and/or other study-related documents. The Principal Investigator will maintain regular written and telephone communication with the Sponsor.

16. DATA MANAGEMENT/RECORD KEEPING**16.1 SOURCE DATA**

All data will be recorded in accordance with GCP, to ensure accuracy, completeness, legibility, and timeliness of the data reported. All data will be recorded directly on the source documents and will be considered source data. PPC standard CRF will be supplied. All the evaluations conducted in this study for each subject will be recorded in the CRF. A hardcopy of each CRF prepared using a data management system with an audit trail, signed by the investigator, will be regarded as the original. All raw data generated in connection with this study, together with the original copy of the final report, will be retained.

Electronic data capture software TrialOne will be available in this study. Partial data will be entered directly onto the CRF to be considered to be source data (e.g. tracking of biosample/data collection, vital signs, investigational drugs administration, meals/fluids uptake status, etc.)

16.2 QUALITY OF DATA

All source documents and laboratory reports will be Quality Control reviewed to ensure accuracy and completeness. AE will be reviewed and assessed for severity and causality by the Principal Investigator/Sub-Investigator. Specific processes of the study, its source documentation and any reports (if applicable) will be audited by the Quality Assurance unit of PPC.

16.3 RETENTION OF DOCUMENTS

All records and documents pertaining to the study will be retained by PPC for at least 2 years after the date of approval of the application or at least 5 years after the date of study termination, and will be available for inspection by the Sponsor and/or Regulatory Agencies.

## 2. STUDY DESIGN

Using a single-dose, randomized, open-label, single-centre, two-way crossover study design, is examined after administration to 60 healthy volunteers under fasting conditions on this study. The subjects are assigned to one of the treatment sequences as follows:

| Sequence | Period 1 | Washout        | Period 2 |
|----------|----------|----------------|----------|
| 1        | T        | $\geq 14$ days | R        |
| 2        | R        |                | T        |

The following tables show the information about study treatments:

### Test Product (T)

|                         |   |
|-------------------------|---|
| Drug name:              | Albuterol Sulfate inhalation aerosol 108mcg per actuation
(equivalent to 90mcg of Albuterol) |
| Active ingredient:      | Albuterol sulfate   |
| Strength:               | eq. to albuterol 90mcg/puff   |
| Dosage form:            | MDI   |
| Manufactured by:        | Intech Biopharm Ltd.  |
| Mode of administration: | Inhalation  |

### Reference Product (R)

|                         |   |
|-------------------------|---|
| Drug name:              | Proair HFA(albuterol sulfate) Inhalation Aerosol 90 mcg per actuation |
| Active ingredient:      | Albuterol sulfate   |
| Strength:               | eq. to albuterol 90mcg/puff   |
| Dosage form:            | MDI   |
| Manufactured by:        | IVAX Pharmaceuticals Ireland Waterford, Ireland                       |
| Mode of administration: | Inhalation  |

The scheduled sampling times for drug's concentration analysis are pre-dose and at 2, 5, 10, 15, 20, 30, 45 minutes, and 1, 1.25, 1.5, 1.75, 2, 2.25, 2.5, 3, 4, 6, 8, 12, 16 and 24 hours after dosing, a total of 22 sampling points are drawn for each study period.

## 3. STUDY OBJECTIVES

### 3.1 Primary Objective

This study is designed to assess the bioequivalence of Albuterol sulfate of the Test product vs. the Reference product under fasting conditions. Bioequivalence will be assumed if the 90% confidence interval of the  $AUC_{0-t}$ ,  $AUC_{0-\infty}$  and  $C_{max}$  ratio are within the 80-125% interval for ln-transformed values.

### **3.2 Secondary Objective**

The other PK-variables will be assessed for descriptive purposes. As for safety parameters, AE and vital signs (BP, PR and body temperature) will be recorded.

## **7. SUBJECT POPULATIONS**

The data from the following subjects will be included in the final pharmacokinetic and statistical analysis:

1. Subjects who complete all study periods.
2. Subjects who have missed samples that have been determined prior to the start of bioanalytical analysis as not significantly impacting the overall outcome of the study.

Data from subjects who were dismissed or withdrew due to AE(s) will not be included in the pharmacokinetic and statistical analysis.

## **8. STATISTICAL METHODOLOGY**

## 8.1 Objective

In this bioequivalence study, the concentration value of Albuterol sulfate for the Test product [Albuterol Sulfate inhalation aerosol 108mcg per actuation (equivalent to 90mcg of Albuterol)] and the Reference product [Proair HFA(albuterol sulfate) Inhalation Aerosol 90 mcg per actuation] will be used to calculate the pharmacokinetic parameters, to perform the statistical analysis, to compare the bioavailability between Test product and Reference product, and will be used to assess the bioequivalence between Test product and Reference product.

## 8.2 General Considerations

### 8.2.1 Continuous Variables

The raw data will be summarized with the number of available observations, mean, standard deviation, minimum and maximum on visit basis.

### 8.2.2 Categorical Variables

The raw data will be summarized with the number of available observations, frequency of each class on visit basis.

## 8.3 Pharmacokinetic Analysis

The following pharmacokinetic parameters will be estimated (where possible) for Albuterol sulfate included in the pharmacokinetic and statistical analysis for the subjects in the final data set:

|                            |   |
|----------------------------|---|
| $C_{\max}$ :               | The maximal observed plasma concentration.  |
| $T_{\max}$ :               | Time when the maximal plasma concentration is observed.   |
| $AUC_{0-t}$ :              | Area under the concentration-time curve from time zero until the last measurable concentration or last sampling time $t$ , whichever occurs first. $AUC_{0-t}$ is estimated using the trapezoidal method. |
| $AUC_{0-\infty}$ :         | Area under the concentration-time curve from time zero to infinity, calculated as $AUC_{0-t} + C_{\text{last}}/\lambda$ , where $C_{\text{last}}$ is the last measurable concentration.                   |
| $k_{\text{el}}(\lambda)$ : | Terminal elimination rate constant, estimated by linear regression analysis of the terminal portion of the ln-concentration vs. time plot.  |
| $T_{1/2}$ :                | Terminal elimination half-life, estimated as $\ln(2)/\lambda$ .   |
| MRT:                       | Mean residence time   |

If a subject's pre-dose concentration is less than or equal to 5% of the  $C_{\max}$  value for that subject in the given period, then the subject's data without any adjustments can be included in all pharmacokinetic measurements and calculations. If the pre-dose value is greater than 5% of the  $C_{\max}$ , data from that subject will be dropped from the pharmacokinetic and statistical analysis.

During pharmacokinetic and statistical analyses, drug concentrations below the lower limit of quantitation (<LLOQ) of an assay will be considered as zero except when they occur between two measurable concentrations where they will be considered as missing during pharmacokinetic calculations and estimations.

Missed samples and non-reportable concentrations (e.g. quantity not sufficient) from the analytical laboratory will be treated as they had not been scheduled for collection in the pharmacokinetic analysis.

The  $AUC_{0-\infty}$ ,  $ke_l(\lambda)$ ,  $T_{1/2}$  and MRT parameters will not be estimated for plasma concentration-time profiles where the terminal linear phase is not clearly defined, only the  $AUC_{0-t}$ ,  $C_{max}$  and  $T_{max}$  will be presented and included in the statistical analysis.

#### 8.4 Statistical Analysis for Pharmacokinetic Parameters

Pharmacokinetic and statistical analysis will be performed by PPC. The actual sampling times will be used in the pharmacokinetic calculations.

Descriptive statistics of all pharmacokinetic parameters (min, max, median, mean, standard deviation and coefficient of variability) will be provided for Albuterol sulfate for the Test and Reference products. Parameter differences will be tabulated without coefficient of variability and geometric mean.

ANOVA including sequence, subjects nested within sequence, period and treatment will be performed on the ln-transformed data for  $AUC_{0-t}$ ,  $AUC_{0-\infty}$  and  $C_{max}$ , and on the raw data for  $ke_l$  and  $T_{1/2}$ .  $T_{max}$  will be analyzed using an additional non-parametric test (Wilcoxon test).

The 90% CI of the Test/Reference ratios of geometric means for  $AUC_{0-t}$ ,  $AUC_{0-\infty}$  and  $C_{max}$  will be calculated based on the LSMEANS and ESTIMATE of the ANOVA. Schuirmann's two one-sided test procedures will be evaluated.

For Albuterol sulfate, the 90% CI of the Test/Reference ratios of geometric means for  $AUC_{0-t}$ ,  $AUC_{0-\infty}$  and  $C_{max}$  will be calculated based on the LSMEANS and ESTIMATE of the ANOVA. Schuirmann's two one-sided test procedures will be evaluated.

If study is carried out in two or more groups of subjects, the model should reflect the fact that the periods for the first group are different from the periods for the second group.

The model of ANOVA including Group, Sequence, Treatment, Subject (nested within Group  $\times$  Sequence), Period (nested within Group), Group-by-Treatment Interaction will be performed on the ln-transformed data for  $AUC_{0-t}$ ,  $AUC_{0-\infty}$  and  $C_{max}$ .

Subject (nested within Group  $\times$  Sequence) is a random effect, and all other effects are fixed effects.

If the Group-by-Treatment interaction test or Group test is not statistically significant ( $p \geq 0.05$ ), the bioequivalence will be demonstrated by pooled group of all subjects.

If the Group-by-Treatment interaction test or Group test is statistically significant ( $p < 0.05$ ), the bioequivalence will be demonstrated by pooled group of all subjects and separated group.

Additional statistical and alternate tests will be performed if necessary.

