9.6 SAMPLE SIZE

For the pivotal study, a sufficient number of healthy adults will be screened with volunteer's consent and 60 subjects will be randomized under fasting conditions.

When possible, subjects will be enrolled in three echelons for all the planned number of subjects. If the capability/capacity of the clinical study facility is limited during the enrollment, the planned subjects may be split into 3 or more echelons with minimal 18 subjects in each echelon. **If the minimal subject number per echelon fails to meet the requirement, it is acceptable to split more echelons to achieve the designated sample size, as specified in the protocol.** In the circumstance the subjects are enrolled in split groups, statistical analysis will NOT be carried out before all the planned subjects have completed the study. Details for considerations of potential group effects will be stipulated separately in the statistical analysis plan.

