## 8.5 Bioequivalence Criteria

Bioequivalence will be demonstrated under fasting conditions if the 90% CI for the Test/Reference ratios of geometric means for  $AUC_{0-t}$ ,  $AUC_{0-\infty}$  and  $C_{max}$  are completely contained within the FDA defined acceptance range of 80.00%-125.00% for Albuterol sulfate.

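### SAP 8.4 lets a Group main-effect test, which says nothing about T/R, send the primary bioequivalence decision to separate groups, with no rule for results that disagree

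*SAP*

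**What the plan says.** Protocol 9.6 plans that, when possible, "subjects will be enrolled in three echelons for all the planned number of subjects". It sets a minimum of 18 per echelon but relaxes it: "it is acceptable to split more echelons to achieve the designated sample size". The handling of groups is deferred: "Details for considerations of potential group effects will be stipulated separately in the statistical analysis plan". SAP 8.4 is therefore the only place where the rule exists.

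SAP 8.4 first gives the ordinary crossover ANOVA and takes the 90% CI from it. For a study run in groups it says the model should allow for periods that differ between groups. It then lists Group, Sequence, Treatment, Subject nested in Group × Sequence (random), "Period (nested within Group), Group-by-Treatment Interaction will be performed on the ln-transformed data". Two branches follow, both at the 0.05 level:

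- "If the Group-by-Treatment interaction test or Group test is not statistically significant": bioequivalence is shown in the pooled subjects.
- "If the Group-by-Treatment interaction test or Group test is statistically significant": "the bioequivalence will be demonstrated by pooled group of all subjects and separated group".

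SAP 8.5 states one criterion, "Bioequivalence will be demonstrated under fasting conditions if the 90% CI for the Test/Reference ratios of geometric means" lies within 80.00%-125.00% for AUC0-t, AUC0-∞ and Cmax. It does not say whether this means the pooled interval, the group intervals or both.

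**The concern.** There are two faults.

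**Wrong trigger.** Each subject receives both products, and T/R is estimated from the difference within a subject. A subject's overall level cancels from that difference, and so does the average level of the echelon. The Group test asks only whether one set of volunteers has higher average exposure than another. Only the Group-by-Treatment test asks whether T/R differs between echelons.

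**Undefined decision.** Once the second branch is entered, the SAP does not say whether every group must pass, whether one is enough, or whether the by-group results are descriptive. It does not say whether the trigger acts endpoint by endpoint or across all three. Nor does it say which model gives the pooled interval: the ordinary ANOVA lacks Period nested in Group, and the only group model contains Group-by-Treatment.

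At stake is the primary conclusion. On the strict reading, a bioequivalent product can fail because echelons of different people differ in average exposure. On a looser reading, the conclusion is chosen after the data are seen. Inflation of the type I error is not claimed, because the second branch still includes the pooled result.

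A smaller point: both branches are joined by 'or', so read literally both apply when exactly one test is significant. Reading the first as 'neither is significant' removes the overlap.

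**Working it through.** **Inputs from the documents:** 60 subjects, allocated 1:1 to TR and RT; three echelons by default (60/3 = 20 each if equal); trigger level 0.05; 90% CI; limits 80.00%-125.00%; three endpoints. The plan gives no CV, expected ratio, correlation or power, so there is no figure of its own to reproduce.

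**Assumed:** true T/R 0.95; within-subject CV 15%-30%, equal across endpoints; between-subject CV 40%; correlation 0.95 between the two AUCs and 0.75 between each AUC and Cmax, varied from 0.99/0.90 to 0.80/0.50.

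**1. Does Group carry information on T/R?** Three groups of 20 were simulated with ln-scale level shifts of 0, 0.2 and 0.4 (between-subject SD 0.4) and the same T/R in each group. The Group test was significant in 74% of trials at CV 20% and 69% at CV 30%. Group-by-Treatment stayed at 5%. The mean estimate of ln(T/R) did not depend on the Group result: -0.051 against -0.051 at CV 20%, and -0.050 against -0.052 at CV 30%.

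**2. How often is the second branch entered with no group effects at all?**

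- One endpoint, two tests: 1 - 0.95² = 9.75%.
- Three endpoints, if independent: 1 - 0.9025³ = 26.5%.
- Three correlated endpoints (simulated): about 18% at 0.95/0.75, and 14%-22% over the correlation range. The Group test alone is responsible in 7%-10% of trials.

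**3. What if one echelon simply has higher exposure?** Let one of three echelons be higher by a factor r, with T/R identical.

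- Variance of a subject's mean = ln(1 + 0.40²) + ln(1 + 0.25²)/2 = 0.1484 + 0.0303 = 0.1787.
- Noncentrality = 20 × (2/3) × (ln r)² / 0.1787, which is 2.48 for r = 1.2 and 5.13 for r = 1.3.
- Power of the F(2, 56) test at 0.05: 26% and 49% per endpoint. With between-subject CV from 50% down to 30%, the range is 19%-69%.

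**4. How likely is disagreement?** Single-endpoint power of the two one-sided tests:

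| CV | Pooled, n = 60 | One group of 20 | All three groups |
|---|---|---|---|
| 20% | 99.9% | 83.5% | 0.835³ = 58.2% |
| 25% | 98.4% | 64.3% | 0.643³ = 26.6% |
| 30% | 93.6% | 43.9% | 0.439³ = 8.5% |

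The last column is the chance that all groups pass. It matters only in trials that enter the second branch and is not the power of the study.

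**5. Overall power if every group must pass once any endpoint triggers** (20,000 simulated trials per cell, correlations 0.95/0.75, no group effects, pooled CI from the model without Group-by-Treatment):

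| CV | Pooled CI decides | Strict reading, interaction trigger only | Strict reading, both triggers | Loss from interaction | Further loss from Group |
|---|---|---|---|---|---|
| 15% | 100% | 95.5% | 94.5% | 4.5 | 1.0 |
| 20% | 99.8% | 91.2% | 86.3% | 8.6 | 4.9 |
| 25% | 96.9% | 87.9% | 80.4% | 9.0 | 7.5 |
| 30% | 88.7% | 80.4% | 72.8% | 8.3 | 7.6 |

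Over the correlation range, the both-triggers column becomes 93%-96%, 82%-89%, 76%-85% and 67%-78%. Applying the rule endpoint by endpoint gives 95.2%, 87.7%, 81.4% and 73.3%. With four echelons of 15, which Protocol 9.6 permits, it gives 88%, 83%, 79% and 73%.

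**The case against.** The strongest reply is that the pooled result already decides. SAP 8.4 keeps the pooled subjects in both branches and never says that each group must pass. Protocol 14.2 analyses all subjects in the final data set, Protocol 14.3 and SAP 8.5 each give a single criterion, and SAP section 10 declares no change from the protocol. On that reading no power is lost, and the losses above are a worst case. They also depend on assumed inputs: on the strict reading, power is still 99.9% at CV 10% and 98.8% at CV 12%. And the Group test causes less than half of the loss at every CV shown.

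Much of this is fair. The power figures are conditional, and the larger share comes from the interaction trigger, which is at least aimed at the right question. A pooled failure is already a failure; only a pooled pass with a failing group is open.

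The reply does not settle the rule. Protocol 9.6 hands group effects to the SAP, so the general protocol sentences cannot decide the matter. The SAP speaks of demonstrating bioequivalence in separate groups, not of displaying results. Both the lenient and the strict reading need words that the SAP lacks. No reading makes the Group main effect informative about T/R.

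**Conclusion.** The concern holds and must be fixed, because the rule governs the primary conclusion and three echelons are the default. That the trigger is wrong and the decision undefined follows from the text and the model, with no numerical assumption.

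The size is conditional on the assumed CVs, true ratio and correlations. The second branch would be entered in about 14%-22% of trials with no group effects, and more often when echelons differ in average exposure. If it requires every group to pass, overall power falls by about 5 to 17 points for CVs of 15%-30% at the central correlations, of which the Group test accounts for about 1 to 8. If by-group results are only supportive, the loss is nil, but the SAP does not say so.

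**What to change.** Remove the Group test from both conditional sentences in SAP 8.4 and replace the two branches with wording such as:

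> The bioequivalence decision rests on the pooled 90% CI of all subjects for AUC0-t, AUC0-∞ and Cmax, from the model with Group, Sequence, Treatment, Period (nested within Group) and Subject (nested within Group × Sequence), without Group-by-Treatment. Group-by-Treatment is tested for each endpoint as a diagnostic, in a separate model that adds this term. If p < 0.05, T/R ratios with 90% CIs are presented by echelon as supportive results and do not replace the pooled decision.

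SAP 8.5 should then say that its criterion applies to that pooled interval.

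The cost is SAP wording only. The downside is that a significant interaction no longer leads to a formal by-group decision, although it is still reported. If the sponsor wants it to keep a decision role, the SAP must state in advance what is concluded when pooled and by-group results disagree, and whether the rule acts per endpoint or across all three.
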